Study Protocol and Statistical Analysis Plan

Modulation of the Intestinal Microbiome by a High Protein Diet

NCT04812964

Document date: April 5, 2018

STUDY PROTOCOL: Modulation of the Intestinal Microbiome by a High Protein Diet

A. Design of randomized, controlled study comparing high and normal protein isocaloric calorie restriction diets for obesity.

Rationale and hypothesis: Based on my preclinical rodent model data, I hypothesize that a high protein diet will shift the composition of the microbiome of obese subjects, including increased *Akkermansia*, and that this will be associated with alterations of the metagenome (bacterial genes) and metabolome.

Study design: This hypothesis will be investigated in a randomized controlled study of the intestinal microbiome of an estimated 216 obese Veterans assigned 1:1 to isocaloric high protein (HPD) or normal protein (NPD) diets. The study will be advertised by posting flyers in the West Los Angeles VA Medical Center MOVE obesity clinic. MOVE physicians will provide interested patients with information about the study. Participants will undergo an initial screening visit in the clinical research unit after their MOVE appointment or on a later date. Once enrolled, participants will return to the clinical research unit for a baseline visit and follow-up visits on weeks 2, 4, 6, 8, 12, and 16 for dietary counseling, physical measurements, phlebotomy, and dietary questionnaires. The recruitment rate is estimated as 7 per month based on the recently completed study led by [name]. Patient recruitment and sample collection will be performed during the first 3 years of the study.

Inclusion criteria: Men and women between 20 and 75 years of age, BMI 27 to 40 kg/m², non-smoker or stable smoking habits for at least 6 months prior to screening and agreement not to change such habits during the study; subjects on non-obesity prescription medication may be included.

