Microbiome analysis: DNA will be extracted from fecal samples collected in ethanol at baseline, day 3, day 7, week 2, day 17 (3 days after calorie restriction), day 21 (7 days after calorie restriction), week 4, week 6, week 8, week 12, and week 16 using the MO BIO Powersoil kit. Sequencing of the 253 base pair V4 region of 16S ribosomal DNA will be performed using the Illumina HiSeq 2500 to a depth of 250,000 reads per sample. Microbial diversity (alpha diversity) will be compared between the two dietary groups at each time point using the Chao1 index, Shannon index, and Faith's phylogenetic diversity. Significance will be determined using a non-parametric test (Mann-Whitney U). Microbial composition (beta diversity) will be compared across all samples using weighted UniFrac (a phylogenetic distance metric) and visualized by principal coordinates analysis (PCoA). Significance of differences in composition at each time point will be determined using Adonis, a permutation-based method. Baseline data will be analyzed to confirm that randomization had successfully eliminated pre-existing microbial differences between the two dietary groups.

Abundance of individual bacteria will then be fitted to multivariate models using DESeq2. This algorithm performs normalization using size factors estimated by the median-of-ratios method, employs an empirical Bayesian approach to shrink dispersion, and fits the data to negative binomial models. Diet group, time point, interaction between diet and time point, baseline BMI, age, sex, and smoking status will be covariates in the model. Diet composition parameters derived from the nutritional instruments (3DFR, FFQ) may also be included. This model will be compared to a reduced model that does not include the diet:time point interaction. A likelihood ratio test will be used to identify microbes with differential abundance by diet at time points after baseline. Estimates of significance will be adjusted for multiple hypothesis testing to calculate q-values, which represents the false discovery rate. Q-values less than 0.05 will be considered significant. Microbes that are differentially abundant on a HPD will be grouped by hierarchical clustering to highlight distinct kinetic patterns of microbial change.

D. Risk/benefit analysis

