1. RISKS TO SUBJECTS

a. Human subjects involvement and characteristics

Human subjects will be recruited from the MOVE Obesity Clinic at the West Los Angeles VA Medical Center within the VA Greater Los Angeles Healthcare System (GLAHS). They will be referred for study enrollment if they meet the inclusion criteria and do not meet any provisions of the exclusion criteria. The inclusion criteria include: men and women between 20 and 60 years of age, BMI 27 to 40 kg/m², non-smoker or stable smoking habits for at least 6 months prior to screening and agreement not to change such habits during the study. The exclusion criteria include weight change of > 3.0 kg in the month prior to screening, weight loss of > 10 kg in the 6 months prior to screening, calorie restriction diet (< 1500 kcal/day) for a period of 4 months or more in the 12 months prior to screening, use of any other investigational drug(s) within 8 weeks prior to screening, abnormal baseline laboratory parameters (serum creatinine > 1.6 mg/dl; ALT, AST, total bilirubin > 2.0 times the upper limit of normal; triglycerides > 500 mg/dl, total cholesterol > 350 mg/dl, TSH outside of normal range), consumption of more than 1 alcoholic beverage per day, pregnancy or intention to become pregnant. Following

informed consent, subjects will undergo randomization to either the normal protein diet or high protein diet groups. Both dietary interventions are consistent with clinical practice for management of obesity and do not pose any appreciable risk to the patient. Subjects will be asked to collect stool eleven times and to visit the VA clinical research unit seven times over 16 weeks.

b. Sources of material

Data and materials collected during the study will be used only according to the protocol approved by the VA Institutional Review Board (IRB). All information will be retained electronically behind the VA's electronic firewall except for regulatory documents and printed informed consent forms. All subjects will receive a unique research identifier number with the identities of the subjects retained only in a code key kept in a secure directory behind the firewall. Stool will be collected by techniques described in Aim 1 of the Research Plan. Demographic and medical data will be collected for all of the subjects according to the study protocol. Only the principal investigator (PI, [name]) and study coordinator will have access to confidential patient information.

c. Potential risks

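### Zero handling in the median-of-ratios size factors is not specified; over up to 2,376 pooled stool samples the standard form is likely to fail or rest on few taxa if the 16S counts are sparse

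*Combined protocol and SAP*

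**What the plan says.** Section A (Study design) plans for "an estimated 216 obese Veterans assigned 1:1". Section D.1.a says "Subjects will be asked to collect stool eleven times". Section C (Microbiome analysis) lists the sequenced samples, beginning "fecal samples collected in ethanol at baseline, day 3, day 7, week 2, day 17", and sets sequencing "to a depth of 250,000 reads per sample".

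The differential-abundance step is in the second paragraph of that section: "Abundance of individual bacteria will then be fitted to multivariate models using DESeq2". The normalization is described as "normalization using size factors estimated by the median-of-ratios method". One model pools the time points: "Diet group, time point, interaction between diet and time point, baseline BMI, age, sex, and smoking status will be covariates in the model". A likelihood ratio test against a model without the interaction identifies the taxa, with q < 0.05 as the threshold. Taxa found to differ are then clustered by kinetic pattern.

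The section does not say whether taxa are sequence variants, genera or another level. It gives no prevalence filter, no rule for zeros in the size factors and no fallback normalization. Neither prevalence nor dispersion is reported anywhere in the documents.

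**The concern.** The standard median-of-ratios estimator divides each count by that taxon's geometric mean over all samples, then takes the median of these ratios within a sample. One zero makes the geometric mean zero, and the taxon drops out of the reference set. The more samples are pooled, the fewer taxa can survive. This plan pools every time point from every participant.

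Two things are at stake:

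- **No taxon survives.** The size factors cannot be computed, and a replacement has to be chosen after the data are in hand.
- **A few survive.** The software runs, but each sample's size factor rests on those few taxa. Its error is shared by every taxon in that sample. If a reference taxon itself responds to diet, the size factor absorbs part of that response and the other taxa appear to move the opposite way. Such a shift differs by arm and time, so it enters the diet-by-time interaction under test, and false-discovery adjustment does not remove it.

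The study hypothesis in section A is that the diet shifts the microbiome, including *Akkermansia*, so stable reference taxa cannot be taken for granted.

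**Working it through.** **Inputs from the documents.** 216 participants (section A); 11 stool collections (section D.1.a); 250,000 reads per sample (section C). Prevalence p, negative binomial dispersion phi and the pattern of absence are not given. They are assumed below and shown as ranges.

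**Sample count.** The times listed in section C are baseline, days 3 and 7, week 2, days 17 and 21, and weeks 4, 6, 8, 12 and 16. That is 11, which agrees with section D.1.a. The planned maximum is 216 x 11 = 2,376 samples. The documents do not print this total, and it assumes no dropout or missed collection.

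**Chance that a taxon is usable.** There are two extremes. If samples are independent, the chance is p^2376. If presence is fixed within a participant, it is p^216.

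| Assumed prevalence | Independent samples | Fixed within participant |
|---|---|---|
| 95% | 1e-53 | 0.002% |
| 99% | 4e-11 | 11% |
| 99.9% | 9% | 81% |
| 99.99% | 79% | 98% |

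Repeated samples from one person lie between the two columns. A 50% chance needs a prevalence of 0.5^(1/2376) = 99.97% or 0.5^(1/216) = 99.68%. Losing 20% of samples (1,900 left) or 40% (1,425 left) raises the independent figure at 99.9% to 15% or 24%. At 99% it stays essentially zero.

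**Effect of sequencing depth.** With mean count mu = 250,000 x relative abundance, the chance of a zero is (1 + mu x phi)^(-1/phi). Take a taxon at 1% abundance that is carried by everyone, so mu = 2,500:

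- phi = 0.5: zero chance 1251^(-2) = 6.4e-7; chance of no zero in 2,376 samples 99.9%.
- phi = 1: zero chance 1/2501 = 0.0004; chance of no zero 39%.
- phi = 2: zero chance 5001^(-0.5) = 0.014; chance of no zero essentially 0.

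**Illustrative simulation of usable taxa** at 250,000 reads, with abundances drawn from a log-normal distribution and five runs per setting:

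| phi | No participant lacks a taxon: of 150 taxa | No participant lacks a taxon: of the top 300 of 2,000 | Some participants lack taxa: either set |
|---|---|---|---|
| 0.25 | 125-140 | 300 | 0-1 |
| 0.5 | 90-103 | 252-269 | 0-1 |
| 1 | 10-19 | 15-19 | 0-1 |
| 2 or 4 | 0 | 0 | 0 |

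**Noise when few taxa remain.** Under an idealised model at phi = 1, the SD of one sample's log size factor is 0.82 with 3 reference taxa, 0.44 with 10 and 0.14 with 100.

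**Bias when one reference taxon responds.** Let the k reference log-ratios be standard normal and raise one of them by 1 log unit. The mean of their median moves by 0.31 for k = 3, 0.18 for k = 5, 0.09 for k = 10 and 0.04 for k = 20. Every other taxon appears to move by that amount in the opposite direction.

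**The case against.** The strongest reply is that failure depends on quantities the documents do not report. The plan refers only to individual bacteria. If these are aggregated or filtered to a near-universal core with low dispersion, the standard estimator works: at phi of 0.5 or below with no participant-level absence, about 90 or more of 150 taxa stayed usable. At 250,000 reads, sampling zeros are also rare for common taxa. And because the samples are 11 repeats per person, the independence column overstates the problem. All of this stands, and it limits the conclusion to sparse counts.

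A second reply is that the sentence describes what DESeq2 does and names no variant. The poscounts option changes only the geometric mean and still takes a median of ratios, so it fits the plan's wording. This also stands: the remedy is to specify the variant, not to abandon the method. It does not close the gap, because a literal reading leads to the standard form.

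A third reply is that having no usable taxa is a visible failure, while the silent bias fades quickly as the reference set grows. The figures for k = 10 and k = 20 bear this out. But a visible failure still leaves the choice of normalization until after data collection.

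A reader might go further and infer that the analysis is certain to fail, or that a particular loss of power follows. The documents support neither. The first needs prevalence and dispersion figures that they do not contain. The second needs a number of surviving taxa that they do not imply, and a simple two-group power calculation would not describe the planned negative binomial likelihood ratio test of the interaction.

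**Conclusion.** The point holds as a specification gap with a likely practical consequence. Read literally, the plan applies an estimator that needs taxa present in all of up to 2,376 samples and makes no provision for zeros. For sparse 16S counts it is likely to be uncomputable or to rest on few taxa. In the range examined, this followed whenever some participants lacked taxa altogether, and at phi of 2 or more in any case. It did not follow for a near-universal, low-dispersion set of taxa.

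The noise and bias figures are illustrations under idealised models, not predictions for this trial. Noise unrelated to diet mainly costs precision. Directional bias needs both a diet-responsive reference taxon and a small reference set.

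The effect is confined to the differential-abundance results, including any for *Akkermansia*, and to the kinetic clustering built on them. The weight-loss comparison, alpha diversity and the UniFrac/Adonis analyses do not use these size factors.

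**What to change.** Amend the DESeq2 paragraph of section C to state:

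1. the taxonomic level at which abundance is modelled;
2. a prevalence filter applied before normalization (for example, taxa present in at least 10% of samples);
3. a zero-tolerant size factor, for example the DESeq2 poscounts option, which takes the geometric mean over positive counts;
4. that the number of taxa driving each size factor will be reported;
5. a sensitivity analysis with one alternative normalization, such as the geometric mean of pairwise ratios.

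The cost is a few sentences, one software option and a repeat run for the sensitivity analysis. No new data are needed. The downside is that some rare taxa are left untested because of the filter.

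### Taxon q-values rest on an uncalibrated negative binomial likelihood ratio test, so the error rate at q < 0.05 can vary by taxon in either direction, and heavy-tailed taxa can fill the list with false positives

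*Combined protocol and SAP*

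**What the plan says.** All of this is in Section C, under Microbiome analysis, unless noted.

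- Model family: DESeq2 "employs an empirical Bayesian approach to shrink dispersion, and fits the data to negative binomial models".
- Terms: "Diet group, time point, interaction between diet and time point, baseline BMI, age, sex, and smoking status will be covariates in the model". No participant term is listed.
- Comparison: "This model will be compared to a reduced model that does not include the diet:time point interaction".
- Test: "A likelihood ratio test will be used to identify microbes with differential abundance by diet at time points after baseline".
- Error rate: "Q-values less than 0.05 will be considered significant". The procedure that turns p-values into q-values is not named.
- Size of the data: Section A plans "an estimated 216 obese Veterans assigned 1:1 to isocaloric high protein (HPD) or normal protein (NPD) diets", and Section D (Risks to subjects) says "Subjects will be asked to collect stool eleven times".

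For individual taxa the plan gives no goodness-of-fit check, outlier rule, robust variance, permutation reference or confirmatory test. For alpha diversity it uses Mann-Whitney, and for beta diversity the permutation-based Adonis.

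**The concern.** The hypothesis to be tested is that a microbe does not differ by diet after baseline. The chi-square reference tests something narrower: no diet difference, negative binomial counts and independent samples, all together. If abundance has a heavier right tail than the negative binomial allows, the likelihood-fitted dispersion falls short of the true variance. A few high samples can then produce a small p-value with no diet effect. Dispersion shrinkage and size factors do not address this, and q-values presuppose valid p-values.

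The study hypothesis names *Akkermansia*, and this model is the only stated test of individual bacteria. Taxa found differentially abundant then go into hierarchical clustering, so false calls would reappear as reported kinetic patterns.

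**Working it through.** **Nothing to reproduce.** The 0.05 is a declared level, not a computed figure. The check is whether the planned test delivers it.

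**Inputs from the documents.** 216 participants, 108 per arm; 11 stools each, so 216 × 11 = 2,376 samples; interaction df = (11 − 1)(2 − 1) = 10, with 5% critical value 18.31.

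**Assumptions.** Poisson counts around log-normal abundance, no diet effect, equal depth, covariates other than diet and time omitted, and Benjamini-Hochberg for q-values. The simulations imitate DESeq2 and do not run the package.

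**Step 1: distribution alone, independent samples.** For large counts and log variance σ², the negative binomial fit settles on dispersion α = 1/k, where ln k − ψ(k) = σ²/2 (ψ is the digamma function). The true squared coefficient of variation is e^{σ²} − 1. The statistic is inflated by about r = (e^{σ²} − 1)/α, and the rejection rate is about P(χ²₁₀ > 18.31/r).

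| log SD | α | true CV² | r | formula, 10 df | simulated, 10 df |
|---|---|---|---|---|---|
| 0.5 | 0.240 | 0.284 | 1.18 | 11% | about 11% |
| 1 | 0.879 | 1.718 | 1.95 | 50% | about 47% |
| 1.5 | 1.80 | 8.49 | 4.72 | 95% | about 88% |

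On truly negative binomial counts the simulations gave 4.6% to 5.5%, so the excess is not a coding fault. Dispersion shrinkage did not remove it. A Cook's-type outlier replacement, which the plan does not mention, moved 45.9% only to 43.3% at log SD 1, and 85.6% to 83.9% at 1.5.

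**Step 2: the trial's structure, 11 stools per person, no participant term.** The dispersion is now fitted to total variation, σ_u² (between persons) plus σ_e² (within person). The interaction compares stools from the same people, so most of the person component cancels. The relevant variance, in units of the squared mean, is e^{σ_u²+σ_e²} − e^{σ_u²} = e^{σ_u²}(e^{σ_e²} − 1). Hence r = e^{σ_u²}(e^{σ_e²} − 1)/α, with α taken at σ² = σ_u² + σ_e². Simulated values use mean count 50.

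| SD person/within | relevant variance | α | r | formula | simulated | null taxa called at q < 0.05 |
|---|---|---|---|---|---|---|
| 1/0.5 | 2.718 × 0.284 = 0.772 | 1.074 | 0.72 | 0.5% | about 0% | 0 of 150 |
| 0.71/0.71 | 1.649 × 0.649 = 1.070 | 0.879 | 1.22 | 13% | 10–14% | 0–2 of 150 |
| 1/0.75 | 2.718 × 0.755 = 2.052 | 1.308 | 1.57 | 31% | 20% | 9–11 of 150 |
| 1/1 | 2.718 × 1.718 = 4.671 | 1.625 | 2.87 | 78% | 57–60% | 64–75 of 150; 193 of 400 in a separate run |
| 1/1.5 | 2.718 × 8.488 = 23.07 | 2.474 | 9.33 | >99% | about 90% | not tabulated |

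Truly negative binomial counts gave 6% in this layout. The formula is a large-sample guide: it gets the direction right but overpredicts at larger SD, so the simulated column is the one to use.

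**Step 3: the other direction.** Zero-inflated negative binomial taxa without a heavy tail, simulated as independent samples, gave rejection rates of 0.0% to 0.3%.

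**Step 4: realised false discovery rate.** In a simpler design (one sample per participant, 1 df, 10% of 300 taxa truly changed twofold) it was 4.8% for negative binomial taxa, 31% at log SD 1 and 66% at 1.5.

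**Step 5: the remedy.** With 11 stools per person, referring the same statistic to whole-participant permutation of diet labels gave 4.0% to 5.5%. On those data the chi-square reference gave 46.7% (log SD 1, no person effect), 10.3% (log SD 1, half the log variance between persons) and 60.0% (log SD 1.5, half between persons). Across all such checks the permutation level was 3% to 6%.

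The number of permutations B matters. The smallest attainable p is 1/(B + 1). For one taxon among m to reach q < 0.05 under Benjamini-Hochberg, 1/(B + 1) ≤ 0.05/m, so B ≥ 20m − 1; for m = 300 that is 5,999. With B = 199 and m = 100, at least 0.005 × 100/0.05 = 10 taxa would have to tie at the minimum, so the absence of calls there is partly granularity.

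**The case against.** The strongest objection is that the premise is assumed. The plan names a standard model, does not contradict itself, and gives no count data or pilot dispersion. That stands: the documents fix neither the size nor the direction of the error. It does not remove the point, because a test whose level runs from near 0% to about 90% over these settings needs calibration.

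Three stronger readings are tempting.

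- A reader might infer that the list will fill with false positives, and take the independent-sample rates as the trial's own. The documents do not support this. The trial takes repeated stools from the same people, and stable person differences can soften the inflation or reverse it (1/0.5 in the table). The independent-sample rates show only that the distributional part exists without repeated sampling.
- A reader might infer that inflation has been shown to persist once participant terms are fitted. It has not. With 216 participant terms and plain maximum-likelihood dispersion, truly negative binomial counts already gave 12% (dispersion 0.3) and 8.5% (dispersion 1.0) in 200 runs, because dispersion is biased low with about 236 parameters. Excess under that model cannot be credited to the tail without such a control. What can be said is that a participant term alone should not be assumed to cure the problem.
- A reader might infer that the whole microbiome hypothesis rests on this list. Section A hypothesises a shift in composition, and Adonis tests that by permutation.

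The overlap with the missing participant term is real, since one edit serves both. The distributional part is nonetheless separate.

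**Conclusion.** The point holds in conditional form. As planned, q < 0.05 can be relied on as a 5% false discovery rate only if counts are negative binomial and samples independent, and nothing in the plan checks or protects against failure of either. Under the log-normal assumption the true level of the nominal 5% test depends on two variances that the documents do not give. Among the settings examined it is near nominal or conservative when within-person variation is small, and badly inflated when within-person log SD is about 1 or more. Because these variances can differ between taxa, q-values on the same list need not be comparable. Confidence is moderate: the mechanism is confirmed by algebra and simulation, but the tail weight of this trial's taxa is unknown. This should be changed before analysis; it does not undermine the design or the data.

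**What to change.** Keep DESeq2 for fold changes and for the interaction statistic. Take each taxon's p-value from re-assigning diet labels 1:1 across whole participants, with all of a person's stools and covariates moving together, and compute q-values from those p-values. If the randomization was blocked or stratified, permute within the same blocks or strata. Specify at least several thousand permutations (see the B ≥ 20m − 1 rule above), or pool permutation statistics across taxa, and name the q-value procedure. State that a taxon is called only on the permutation p-value.

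This follows the unit of randomization, extends the permutation approach already planned for beta diversity, and also repairs the missing participant link.

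A mixed model on log-ratio abundance could serve as a sensitivity analysis, but only if it specifies within-person serial correlation and zero handling. A within-person log-scale F test that ignores serial correlation had size 8–11% when correlation half-lives were 7 to 56 days.

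Cost: SAP wording and computing time, with no new data. Some taxa may no longer be called, and fold changes and p-values will rest on different references.

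### The DESeq2 model does not link the up to 11 stool samples from one participant, so its diet-by-time test is inefficient and its calibration at q < 0.05 is not assured

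*Combined protocol and SAP*

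**What the plan says.** Section C, Microbiome analysis, sequences stool at "baseline, day 3, day 7, week 2, day 17 (3 days after calorie restriction), day 21 (7 days after calorie restriction), week 4" and then at weeks 6, 8, 12 and 16. That makes 11 occasions, and section D.1.a gives the same number of collections.

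Individual bacteria are analysed with DESeq2, which "employs an empirical Bayesian approach to shrink dispersion, and fits the data to negative binomial models". The model terms are listed: "Diet group, time point, interaction between diet and time point, baseline BMI, age, sex, and smoking status will be covariates in the model". One optional extension is named: "Diet composition parameters derived from the nutritional instruments (3DFR, FFQ) may also be included". The test is a likelihood ratio comparison: "This model will be compared to a reduced model that does not include the diet:time point interaction". The decision rule is: "Q-values less than 0.05 will be considered significant". The hits are then used further: "Microbes that are differentially abundant on a HPD will be grouped by hierarchical clustering to highlight distinct kinetic patterns of microbial change".

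No part of the document gives this model a participant factor, random effect, within-person covariance, clustered variance or participant-level permutation.

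**The concern.** All time points are fitted together, so each participant can supply up to 11 observations. The question is whether the two diets differ in their change over time, which is a contrast within people. The model has no way to separate a person's stable level of a taxon from sample-to-sample variation. Both go into one dispersion, and that dispersion is the yardstick for the diet-by-time test. The listed covariates describe types of people and do not identify whose sample is whose. Diet composition parameters do not identify this either.

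This is the plan's only test of individual bacteria, and the hypothesis in section A names *Akkermansia*. If the yardstick is wrong, real shifts can be missed, the q-values need not mean what they say, and the kinetic clustering inherits the result.

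**Working it through.** **Inputs from the document.** 216 participants, 1:1, so 108 per arm (section A); 11 samples each (sections C and D.1.a); negative binomial model, likelihood ratio test, q < 0.05 (section C). The document gives no power, effect size, variance or correlation for this test, so there is no stated figure to reproduce beyond the sample count: 216 × 11 = 2,376 at most.

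**Assumptions.** Time is coded as 11 categories, so the test has 10 df (critical value 18.31 at 5%). All correlations, spreads, dispersions and effects below are assumed. Unless stated, the simulations omit the four baseline covariates and DESeq2's shrinkage across taxa.

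**1. Stable personal level, Gaussian approximation.** With equal variances and exchangeable correlation ρ, the fitted variance estimates the total σ², but the contrast varies only with σ²(1 − ρ). Under the null the planned statistic behaves as (1 − ρ)χ²₁₀, so the true size is P(χ²₁₀ > 18.31/(1 − ρ)):
- ρ = 0.3: threshold 26.16, size about 0.4%
- ρ = 0.5: threshold 36.62, size about 0.01%
- ρ = 0.7: threshold 61.03, size effectively 0

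**2. Same structure, simulated counts with exact negative binomial margins.** Power is for a log fold change of 0.3 in one arm from the first post-baseline sample.

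| ρ | Planned test, null rejection | Planned test, power | With participant effects, power |
|---|---|---|---|
| 0 | 5.3% | 24.8% | 20.5% |
| 0.3 | 0.8% | 9.5% | 31.5% |
| 0.5 | 0.0% | 4.2% | 37% |
| 0.7 | 0.0% | 0.2% | 57.5% |

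The planned test used 2,000 null and 400 power runs; the participant-effects model used 200 of each. For ρ = 0.3 to 0.7 the participant-effects null rejection was 3.5–7.5%. The ρ = 0 row shows that the simulation is sound.

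**3. Participants who change differently over time.** With log-scale slopes of SD 0.7, 1.0 and 1.5 per 16 weeks, the planned test rejected 6.8%, 12.3% and 28.0% under the null. With a person-specific shift at calorie restriction (SD 1.2) it rejected 24.2%. Part of this excess comes from margins that are not negative binomial and from variance that grows over time. The cleaner case keeps negative binomial margins, with correlation 0.8 within each diet phase and 0 between phases. It rejected 7.0% at nominal 5% and 1.25% at nominal 0.1% (800 runs). The effect of correlation alone is thus modest at 5% and clearer in the tail, where q-values are decided.

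**4. Skewed spread between people, kept separate.** Here the person effect is log-normal, with log-SD 0.7 / 1.0 / 1.3 and mean count 100. The last column uses the same margins with every sample drawn independently, so there is nothing to link.

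| Dispersion | Planned test, null rejection | Independent draws, null rejection |
|---|---|---|
| 0.6 | 4.0% / 7.6% / 17.7% | 31% / 60% / 83% |
| 0.3 | 0.2% / 0.7% / 2.4% | 29% / 58% / 81% |

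A repeat put the independent-draw range at 28–84%. Sharing the effect within a person lowers rejection, so the excess here is distributional misfit and not the missing link. A participant term does absorb it: blocked null rejection was 4.7–5.5% in all six settings.

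**5. Is a participant term enough?** With person log-SD 1.0, dispersion 0.3 and added serial correlation decaying over 7 / 28 days, null rejection was:
- planned: 13.0% / 6.5%
- participant blocked: 10.1% / 7.8%
- blocked statistic, diet labels permuted between participants: 4.5% / 4.8%

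Under person-specific slopes, blocking alone rejected about 11% and 19% (120 runs each).

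**6. Does dispersion shrinkage help?** Residual df are about 2,376 − 22 diet-by-time cells − 4 covariates = 2,350. The sampling variance of the log dispersion is about trigamma(1,175) = 0.00085, an SD of about 0.03. The dispersion is already precise, so shrinkage has little to correct. It estimates the wrong quantity for this contrast.

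**The case against.** A reader might infer the familiar form of the problem: repeated samples treated as independent, hence a list filled with false discoveries well above 5%. The documents do not support that. They give no variance inputs, and for a stable personal level with fitting margins the effect runs the other way. The large excesses in step 4 need an assumed log-normal misfit and are larger still when no samples are linked at all. False discovery rates simulated under that assumption would measure the misfit and should not be reported as the cost of the omission.

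Three further objections have force:
- **Calibration may be acceptable for some taxa.** At dispersion 0.6 and log-SD 0.7 the planned test rejects 4.0%. It cannot be said that every q-value is wrong.
- **A participant term alone can calibrate no better.** With 28-day decay, blocking rejects 7.8% against 6.5% for the planned test. This stands, and it determines the fix.
- **Scope is narrow.** The primary clinical endpoint is weight loss. Overall composition is tested separately: "Significance of differences in composition at each time point will be determined using Adonis, a permutation-based method". That test and the Mann-Whitney comparisons of alpha diversity use one sample per person at each time and are unaffected, as are the clinical endpoints.

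None of this supplies the missing link. A participant term cannot be read into the plan either: as a blocking factor it would be aliased with diet group, BMI, age, sex and smoking, all of which are listed.

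**Conclusion.** The point stands in a limited form and should be fixed. The omission is certain from the text. It follows that the diet-by-time test uses a variance that does not match its contrast and is inefficient when people differ stably. Under that structure, with negative binomial margins, it is too strict (about 0–1% at nominal 5% for correlations of 0.3 to 0.7). It can be too liberal when participants drift or shift differently. Skewed between-person spread can also make it too liberal, but through misfit. Direction and size for any real taxon are unknown, so the supportable statement is that calibration of q < 0.05 is not assured, and not that it fails by a given amount. The consequence is confined to the taxon-level screen, including *Akkermansia*, and the clustering that it feeds.

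**What to change.** Add to section C, Microbiome analysis: *Samples from the same participant will be linked in the model. P-values for diet by time will be obtained by permuting diet labels between whole participants.* Then name one model:

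- **DESeq2 with participant as a blocking factor:** participant + time + diet:time against participant + time. Remove the diet main effect, BMI, age, sex and smoking, which are aliased with participant, and state a rule for participants whose counts for a taxon are all zero.
- **Negative binomial mixed model:** a participant random intercept, the listed fixed effects, and the same full-versus-reduced comparison. This option was not simulated here.

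Permutation should be the primary source of p-values and not a fallback, because step 5 shows that a participant intercept alone does not restore the error rate under serial correlation or person-specific trends. Keep q < 0.05.

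**Cost.** No new participants or samples. Blocking departs from the listed covariates and estimates about 216 + 10 + 10 = 236 coefficients per taxon; the mixed model departs from DESeq2. Permutation adds computing: for an assumed 200 taxa, reaching p = 0.05/200 = 0.00025 takes at least 1/0.00025 = 4,000 permutations. With blocking, the reduced model contains no diet term and is fitted only once per taxon.
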